Title: Comparison of Etomidate Plus Propofol, Etomidate Alone on Induction of Anesthesia

NCT03820388

Document Date: March 15, 2017

1) **Protocol Title**

Comparison of Etomidate Plus Propofol vs. Propofol, Etomidate Alone on Induction of Anesthesia, a Pilot Observational Study

Protocol Version Date: 5/2/2017

2) Objectives

The purpose of this study is compare of etomidate plus propofol vs. propofol or etomidate alone during induction of anesthesia.

The specific aims or objectives are testing patient reactions during induction, and in the post anesthesia care unit (PACU).

The hypotheses to be tested: induction with etomidate combined with propofol when compared to induction with propofol or etomidate alone:

1. will provide less pain during injection,

2. less hypotension (compare to propofol), less hypertension (compare to etomidate) and better hemodynamics than propofol or etomidate during induction,

3. Similar postoperative nausea and vomiting (PONV) when compared with propofol and less PONV when compared with etomidate,

4. Similar pain score among all three groups

3) Background

Induction of anesthesia is a critical part of anesthesia practice. Sudden hypotension, hypertension, arrhythmias, and cardiovascular collapse are threatening complications following injection of induction agent in hemodynamically unstable patients. It is desirable to use a safe agent with fewer adverse effects for this purpose.

Both etomidate and propofol are the most commonly used induction agents for general anesthesia (GA) and both propofol and etomidate have their advantages and disadvantages. Propofol has been associated with injection pain, significant hemodynamic change (hypotension) during induction and less PONV. Etomidate has been associated with more stable hemodynamic and less pain during induction, but more myoclonic movements at induction and PONV. However, those findings are still controversial and the published results are still inconsistent.

In a large retrospective study, the authors found that anesthetic induction with etomidate, rather than propofol, is associated with increased 30-day mortality and cardiovascular morbidity after noncardiac surgery. The recommended bolus induction dose is 1.5-2.5 mg/kg for propofol and 0.15-0.4 mg/kg for etomidate. One study showed that etomidate plus propofol had few effects on respiration and circulation in providing sedations for patients undergoing gastroscopy and was safer and more effective than propofol alone. In another study the authors found that with the etomidate-propofol combination (Etofol), a

milder hemodynamic response was determined compared to propofol and etomidate used alone, both at anesthesia induction and after the intubation. Etofol can be a valuable alternative in patients where cardiovascular fluctuations are not wanted. Since there are very limited published results available, it is important to provide more evidence and address the question of whether etomidate plus propofol is better than propofol or etomidate alone on induction of anesthesia.

References:

1. British Journal of Anaesthesia 110 (3): 388–96 (2013)

2. Zhou X. et al. Etomidate plus propofol versus propofol alone for sedation during gastroscopy: a randomized prospective clinical trial. Surg Endosc. March 22, 2016. DOI 10.1007/s00464-016-4861-6

3. J Cardiovasc Thorac Res, 2015, 7(4), 134-140 4. Anesth Analg. 2013 Dec;117(6):1329-37)

4) Inclusion and Exclusion Criteria

Patients will be screening for eligibility through local electronic medical record (EMR) review using the IRB-approved HIPAA Waiver for Authorization for participant identification and recruitment.

The inclusion criteria are:

- Patients scheduled for elective non-cardiac surgery
- ASA physical status of 2 or 3
- Age equal to or greater than 18 years old

Patients who do not meet the above criteria or patients who are in the following specific populations will be excluded:

- Adults unable to provide consent
- Age less than 18 years old
- Pregnant women
- Prisoners
- Difficult airway (Mallampati class 4)
- Morbid obesity (Body Mass Index (BMI) equal or greater than 40
- Preoperative sedation use (benzodiazepines, opioids)
- Severe cardiac (heart block, tachycardia, bradycardia, patient with pacemaker/AICD, pulmonary and liver diseases
- Hypotension and shock
- Emergency surgeries
- Allergy to propofol or etomidate

5) Study Timelines

Patients will be participating in the study for the duration of their surgery and for 24 hours after induction.

We anticipated it to take 1 year to enroll all study subjects.

We anticipate an extra 12 months after completion of the study for the investigators to complete the primary analyses.

6) Study Endpoints

The primary endpoints include:

- 1. Blood pressure changes during induction
- 2. Heart rate changes during induction

The secondary endpoints include:

- 1. Pain at injection
- 2. Myoclonic movements
- 3. PONV in PACU
- 4. Postoperative pain score
- 5. Incidence of adverse reactions during induction
- 6. Severity of adverse reactions during induction

7. Dose and frequency of vasoactive agents and other concomitant medications used to treat adverse reactions of propofol / etomidate

8. Sedation depth using bispectral index (BIS)

- 9. Eyelash reflex disappear time
- 10. Intubation time
- 11. Dose and frequency of analgesic and other sedatives used

7) **Procedures Involved**

This is a non-blinded, randomized, parallel-group study in patients scheduled for elective surgery under general anesthesia and orotracheal intubation to compare etomidate plus propofol vs. propofol or etomidate alone on induction of anesthesia.

There will be three cohorts of 25 patients per cohort with one cohort administered propofol, one cohort administered etomidate, and one cohort administered propofol

etomidate. The sample size was calculated with the blood pressure change \pm 20 mmHg, SD \pm 25 mmHg, power of 0.80 and p value of 0.05 and resulted 25 in each group.

The research team will create 75 envelopes. Each will be numbered, 25 will be in propofol group, 25 will be in etomidate group and 25 will be in propofol/etomidate group. On the day of surgery, one envelope will be randomly picked for each participant.

Patients in the three cohorts will be administered a 30 second bolus by manual hand push.

Intensive PD and safety assessments will be performed prior to dosing on Day 1 until 24 hours post-dose (Day 2). There are no plans for long-term follow-up past the 24 hours.

Three cohorts are as follow:

- 1. Propofol group: 2 mg/kg propofol
- 2. Etomidate group: 0.3 mg/kg etomidate
- 3. Propofol plus etomidate group: 1mg/kg propofol plus 0.15mg/kg etomidate.

Systolic blood pressure, diastolic blood pressure, mean arterial pressure, heart rate will be monitored and recorded before induction, at induction and intubation followed by 1, 3, 5 and 10 minutes after intubation.

Pain on injection will be measured using 4 graded scale; 0 --- no pain, 1 --- verbal complaint of pain, 2 --- withdrawal of arm, 3 --- both verbal complaint and withdrawal of arm.

The incidence and degree of myoclonic movements also recorded as follows: 0 = no myoclonic movements, 1 = minor myoclonic movements, 2 = moderate myoclonic movements, 3 = major myoclonic movements.

The medications used in the 3 groups are clinically used already with FDA approval for their use. This is an observational study and we will compare the effects of the three groups with their medication uses on the parameters we listed above: systolic blood pressure, diastolic blood pressure, mean arterial pressure, heart rate, pain on injection, myoclonic movements, PONV and BIS numbers.

Non-English speaking participants are still eligible for the study. We will use translation services in line with HRP 090 and HRP 091 and the consent short form to enroll interested non-English speaking participants. If we find that we have enrolled 2 patients of a particular language using the short form as the study progressed, we will obtain full translation of the consent form into that language through the use of UCD Translation Services.

8) Data and/or Specimen Management and Confidentiality

All data will be summarized using descriptive statistics. Summaries of continuous variables will present mean, median, standard deviation, minimum, and maximum; summaries of categorical variables will present frequencies and percentages. All data will be presented in subject data listings.

Subject enrollment and disposition, including reasons for early withdrawal from the study, will summarized by group.

Demographic variables will be summarized by group for all enrolled subjects. Data will be stored up to 3 years after finishing the study.

This is a pilot study with a proposal to enroll 25 patients into each group for a total of 75 patients randomized.

We expect to complete data analysis on 20 patients in each group for a total of 60 patients due to patient withdrawal either voluntarily or due to formal withdrawal criteria, ie difficulty with securing patient airway.

9) Provisions to Monitor the Data to Ensure the Safety of Subjects

As this is a minimal risk study, there are no plans to monitor the data.

10) Withdrawal of Subjects

The PI and research team can withdraw subjects from the study without their consent if difficulty securing their airway is encountered.

11) Risks to Subjects

The potential risks are breack to confidentiality and risks associated with the study drugs, Propofol and Etomidate.

In order to safeguard our patient's confidential data and to lessen the likelihood of a breach of confidentiality, the following parameters will be put in place:

- 1. The data will be stored in the PI's password-protected computer in his locked office.
- 2. We don't anticipate needing to transport any data, but if need be, the data will be transported via a hospital issued, password protected IRONKEY.
- 3. Patients' names and medical record numbers will be used initially. A numerical number (0001 to 0050) will be assigned to each patient.

- 4. If the data need to be transmitted, the UCD secured email system will be used and the receiving end needs to be same secured email system.
- 5. Only the research team members can access the data.

Risks associated with Propofol and Etomidate :

Risk of Etomidate:

Transient venous pain on injection

Transient Skeletal muscle movements

Respiratory System: Hyperventilation, hypoventilation, apnea of short duration, laryngospasm, hiccup and snoring suggestive of upper airway obstruction.

Circulatory System: Hypertension, Hypotension, tachycardia, bradycardia, arrhythmias

Risks of Propofol:

Cardiovascular: Bradycardia, arrhythmia, tachycardia, hypotension, decreased cardiac output

Central nervous system: movement

Metabolic/Nutritional: Hyperlipemia

Respiratory: Apnea, respiratory acidosis during weaning

Skin and appendages: Rash, pruritus

12) Potential Benefits to Subjects

Both propofol and etomidate are used in everyday clinical practice. There are still controversial over which out of the two is better. By using the combination of etomidate and propofol at a reduced dosage in cohort 3, we hope that patients can benefit from those drugs through the minimization of side effects.

We are unable to tell if there will be a direct benefit to the study participant.

13) Multi-Site Research

N/A

14) Community-Based Participatory Research

N/A

15) Sharing of Results with Subjects

There are no plans to share study results with participants.

16) Prior Approvals

N/A

17) Provisions to Protect the Privacy Interests of Subjects

Eligible patients will be screened through electronic medical record review up to 48 hours before their scheduled elective surgery. Patients will be approached on the day of the surgery in the UC Davis preoperative holding area of the main hospital to gauge for study interest. Research team will obtain consent from interested participants and honor any withdrawal requests based off of randomization group or time-constraints.

This observational study does not allow for any interventions nor study procedures outside of the patient's normal care, so we will limit unnecessary interactions with the patients to minimize the sense of intrusiveness a subject might experience in response to standard questions, examinations, and procedures.

The research team will complete the HIPPA and required CITI training. Only at the time of data collection can the research team access the necessary patient's information.

18) Compensation for Research-Related Injury

There is no compensation for participating in this minimal risk study.

19) Economic Burden to Subjects

Both medications are already routinely ordered and administered, and will be billed accordingly to the patient's insurance.

20) Drugs or Devices

This is an observational study using FDA-approved medications that are used in everyday practice for anesthesia induction purpose.

Medication is routinely stored in PYXIS and will be taken by the anesthesiology.

21) ClinicalTrials.gov Registration

Section 1: NIH Funded Studies

If yes to BOTH, the study must be registered on Clinicaltrials.gov.

Yes	
	This study is funded by the NIH . (If this study is not funded by NIH, go to
	Section 2.)
	One or more human subjects will be prospectively assigned to one or more
	interventions (which may include placebo or other control) to evaluate the effects
	of those interventions on health-related biomedical or behavioral outcomes.

Section 2: Studies subject to FDA jurisdiction

If yes to ANY the study must be registered on Clinicaltrials.gov.

 This is a prospective clinical study of health outcomes in human subjective compares an intervention with an FDA-regulated device against a correst is not a small clinical trial to determine the feasibility of a device, or a small clinical trial to determine the feasibility of a device. 	jects that ontrol. This a clinical
trial to test prototype devices where the primary outcome measure relation feasibility and not to health outcomes.	elates to
This is a pediatric postmarket surveillance of a device as required und 522 of the Federal Food, Drug, and Cosmetic Act.	nder section
This is a controlled clinical investigation, other than a phase I clinical investigation, of a drug subject to section 505 of the Federal Food, [name] or to section 351 of the Public Health Service Act.	l Drug, and

To view a flowchart describing applicable clinical trials subject to FDA jurisdiction click here.

Section 3: Publishing the results

If yes to BOTH the study must be registered on Clinicaltrials.gov.

Yes	
\boxtimes	This study prospectively assigns people or a group of people to an intervention,
	with or without concurrent comparison or control groups, to study the cause-and-
	effect relationship between a health-related intervention and a health outcome.
\boxtimes	The PI has access to and control over all the data from the clinical trial and has
	the right to publish the results of the trial and plans to publish the results in a
	journal that follows the ICMJE recommendations.

This requirement includes studies of behavioral interventions.

Section 4: Registration on Clinicaltrials.gov is not required

Yes					
	I have read sections for this research.	1-3 above and	l registration	on clinicaltrials.gov	is not required

22) Criteria for 10 Year Approval

If yes to all items below this research may qualify for a 10-year approval period.

Yes	
\boxtimes	This research involves no more than minimal risk.
\boxtimes	This research does not receive any federal or state government funding or funding
	from a private funder who requires annual review per contract.
	This research is not subject to FDA jurisdiction.
\boxtimes	This research does not include prisoners as participants.
\boxtimes	This research is not part of an IRB reliance.
\boxtimes	This research is not subject to SCRO oversight.
\boxtimes	This research is not subject to oversight by the Research Advisory Panel of
	California (RAP of C).
\boxtimes	This research does not involve identifiable information held by the State of
	California Department or Agency
\boxtimes	This research does not involve personnel supported by federal training, center, or
	program grants.
\boxtimes	No personnel involved in the design, conduct, or reporting of this research have a
	financial interest (RFI) in this study.

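### Secondary endpoint 7, on its natural reading, counts a vasoactive dose only after an open-label judgement of why it was given; counting every dose in a fixed window removes that step cheaply

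*Protocol*

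**What the plan says.** Protocol section 6 (Study Endpoints) lists as secondary endpoint 7: "Dose and frequency of vasoactive agents and other concomitant medications used to treat adverse reactions of propofol / etomidate". Endpoint 11 in the same list carries no condition on reason or cause: "Dose and frequency of analgesic and other sedatives used".

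Protocol section 7 (Procedures Involved) states: "This is a non-blinded, randomized, parallel-group study". It sets the blood pressure and heart rate readings from before induction to 10 minutes after intubation. Its list of parameters to be compared covers haemodynamics, injection pain, myoclonus, PONV and BIS, and leaves out vasoactive drug use.

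Protocol section 8 plans descriptive summaries: mean, median, standard deviation and range for continuous variables, counts and percentages for categorical ones, and patient-level listings. It expects 20 patients per group in the analysis. Section 9 plans no data monitoring.

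The SAP has a general sentence on chi-square and Fisher tests for categorical data and a general linear model for haemodynamics. It does not mention endpoint 7.

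**The concern.** As worded, endpoint 7 filters doses through two judgements. Was this dose given for an adverse reaction? Was that reaction due to the induction drug? Both are matters of opinion in the minutes around induction and intubation, when a change in pressure or rate may have more than one cause. Whoever decides knows which drug the patient received.

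Vasoactive treatment alters the blood pressure and heart rate that the trial measures, so readers will want its use by arm beside the primary results. If the count has already been filtered by an arm-aware judgement, a difference between arms may reflect true use, or classification, or both, and the reported figures cannot tell these apart.

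**Working it through.** This is mainly a check of wording. The plan gives no figure for endpoint 7 to reproduce.

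**1. What the qualifier covers.** There are two grammatical readings of endpoint 7.
- *Reading A:* the clause on purpose and cause governs both vasoactive drugs and the other medications. The word *other* places the two in one class, which favours this reading. Endpoint 11 shows that the protocol uses plain wording where no filter is meant.
- *Reading B:* the clause governs only the other medications. All vasoactive doses then count, and the judgement remains only for the rest.

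Reading A is the more natural, but the text does not exclude B.

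**2. Whether anything in the plan fixes the judgement.** I looked in both documents for each item that could do so:

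| Item | Found? |
|---|---|
| Definition of adverse reaction for this endpoint | No |
| Blood pressure or heart rate trigger for treatment | No |
| Counting window for endpoint 7 | No |
| Causality rule | No |
| Blinded assessor or adjudicator | No |

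Since the trial is not blinded, inclusion under Reading A rests on a judgement made with the arm known.

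**3. Size per patient.** Input: 20 analysed per arm (protocol section 8). One patient counted or not counted shifts that arm's rate by 1/20 = 5 percentage points. The dose half of the endpoint is distorted too, because an excluded dose also leaves the dose summary. The documents give no doses, so that effect cannot be sized.

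**4. Sensitivity under assumed rates.** The documents give no rate of vasoactive use. Assume that the same number k of 20 patients in every arm truly receives a given class of drug, and that some are left out in one or two arms. The k values are assumptions. Any gap is then purely an artefact.

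| Counted (of 20 each) | Assumed true k | Test | p |
|---|---|---|---|
| 4 vs 2 | 4 | Fisher, two arms | 0.66 |
| 6 vs 1 | 6 | Fisher, two arms | 0.09 |
| 4 vs 0 | 4 | Fisher, two arms | 0.11 |
| 5 vs 0 | 5 | Fisher, two arms | 0.047 |
| 0, 4, 4 | 4 | exact, three arms | 0.11 |
| 0, 5, 5 | 5 | exact, three arms | 0.036 |
| 0, 0, 4 | 4 | exact, three arms | 0.030 |
| 1, 1, 6 | 6 | exact, three arms | 0.039 |

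For 4 vs 2 the false gap is 4/20 − 2/20 = 10 points, with a Newcombe 95% interval of −13 to 33 points.

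Modest misclassification therefore shifts the reported rates without reaching significance. Heavy misclassification can cross 0.05, and it need not be total: in the 1, 1, 6 case one patient is still counted in each affected arm. These are chosen scenarios with no probabilities attached, so they do not show how likely a false significant result is.

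**The case against.** **The reading is not certain.** Under Reading B the concern about vasoactive drugs disappears. This stands, and the conclusion is worded to allow for it.

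**The endpoint carries little weight.** It is one of 11 secondary endpoints in a self-described pilot, it is not among the compared parameters in section 7, and the SAP gives it no dedicated analysis. This stands and limits the importance of the point.

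**Listings would show the doses.** Section 8 promises patient-level listings of all data. That helps only if doses not attributed to the study drug are recorded, which the documents do not say.

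**The remedy is a trade.** Counting everything turns a measure of treated drug reactions into one of total use, and lets in doses given, for example, in response to laryngoscopy. A sponsor could reasonably prefer the narrower measure. The answer is to report both, with the objective count first.

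**A stronger reading is tempting.** The etomidate risk list has "Circulatory System: Hypertension, Hypotension, tachycardia, bradycardia, arrhythmias", the propofol list has "Cardiovascular: Bradycardia, arrhythmia, tachycardia, hypotension, decreased cardiac output", and hypothesis 2 predicts "less hypotension (compare to propofol), less hypertension (compare to etomidate) and better hemodynamics than propofol or etomidate during induction". A reader might infer that pressure-lowering doses would be counted under etomidate and dropped under propofol. The documents do not support that. Nothing ties the risk lists to endpoint 7, whose slash can be read as naming the study drugs jointly. Hypotension, bradycardia, tachycardia and arrhythmia are on both lists. The Background names hypertension without singling out a drug: "Sudden hypotension, hypertension, arrhythmias, and cardiovascular collapse are threatening complications following injection of induction agent in hemodynamically unstable patients". No direction of bias can be drawn from this.

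**Conclusion.** The point holds in a limited form. On the more natural reading, endpoint 7 makes inclusion of a vasoactive or other dose depend on an indication and attribution judgement made with the arm known. On the alternative reading, this applies only to the other concomitant medications. Nothing in either document removes the judgement.

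The documents establish a risk of bias, not a bias: its direction and size are unknown. The one firm figure is 5 percentage points per patient reclassified, which assumes the expected 20 analysed per arm. A reader might take the sensitivity figures as showing that a false significant result is likely, or that it is unlikely; they support neither, because the rates are assumed and the scenarios selected.

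The effect is confined to the frequency and dose of this one secondary endpoint. The primary blood pressure and heart rate endpoints do not use this classification. I would class the change as a cheap improvement, for the sponsor to consider.

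**What to change.** Redefine endpoint 7 as every vasoactive dose given from the start of the study bolus to 10 minutes after intubation, whatever the reason. The end of this window matches the last scheduled blood pressure and heart rate reading in section 7. It is a proposal, since endpoint 7 states no window of its own.

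- Record drug, dose and time for each.
- Report drugs that raise pressure or rate separately from those that lower it, by arm.
- Keep the subset judged to be treatment of a drug reaction as a descriptive listing, so the present endpoint can still be shown.
- List other concomitant medications separately.
- State in the report that the decision to treat was itself unblinded.

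**Cost.** One sentence in the endpoint list and a few fields on the data form, with no added patients or visits. This assumes that doses are charted during the case, which the documents do not say.

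**Downside.** Some counted doses will have nothing to do with the study drug. The change removes the classification step only. The decision to treat would still be made with the arm known, and limiting that influence would need treatment thresholds set in advance, which this fix does not include.

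### Nothing in the plan keeps the assigned arm from the patient, so injection pain, nausea and postoperative pain are open to expectation bias, and withdrawal by arm can unbalance every comparison

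*Protocol*

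**What the plan says.** - **Blinding.** Protocol Section 7: "This is a non-blinded, randomized, parallel-group study". Neither document masks the patient, the person grading injection pain, or PACU staff.
- **Assignment.** Section 7: "On the day of surgery, one envelope will be randomly picked for each participant". It does not say who opens the envelope, where, or whether the patient is told the result.
- **Contact and withdrawal.** Section 17: "Patients will be approached on the day of the surgery in the UC Davis preoperative holding area". After consent, the team will "honor any withdrawal requests based off of randomization group or time-constraints".
- **Injection pain.** Section 7: "Pain on injection will be measured using 4 graded scale", with grades "0 --- no pain, 1 --- verbal complaint of pain, 2 --- withdrawal of arm, 3 --- both verbal complaint and withdrawal of arm". No rater is named.
- **Other patient-dependent outcomes.** Section 6 lists PONV in PACU and "Postoperative pain score" as secondary endpoints. Neither document gives a scale or an assessor for them.
- **Primary endpoints.** Section 6 lists "Blood pressure changes during induction" and the corresponding heart rate changes.
- **Attrition.** Section 8 randomises 25 per group and expects to analyse 20, naming voluntary withdrawal as one cause. Reasons for early withdrawal are to be summarised by group. The SAP allows for 20% dropout and defines no analysis population.

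**The concern.** A patient can ask to leave because of the assigned group only if the group is known. Consent and assignment both take place on the day of surgery, so a patient may go into induction awake and aware of the arm.

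Two separate problems follow.

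1. **Reporting.** Hypotheses 1, 3 and 4 in Section 2 concern injection pain, PONV and pain score. The protocol itself carries expectations about the arms: Section 3 links propofol to injection pain and etomidate to PONV, and Section 12 hopes the combination will minimise side effects. Patients or staff who know the arm and share such expectations may report or score accordingly. An observed difference could then not be attributed to the drug alone.
2. **Selective loss.** If patients leave because of the arm they drew, those who remain are no longer a randomised comparison. This reaches the primary haemodynamic endpoints as well, even though they are instrument readings.

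**Working it through.** **Can patients learn their arm?** Set the passages side by side. Section 7 has no masking and assigns by envelope on the day. Section 17 places the approach to patients in preoperative holding that same day and accepts withdrawal on grounds of group. The Section 17 clause works only if the patient can know the group. Disclosure before induction is therefore the natural reading, but it is an inference.

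**Which outcomes are exposed?**

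| Outcome | Rank | Source of the score | Exposed to |
|---|---|---|---|
| Injection pain | Secondary | Verbal complaint and arm withdrawal, graded by an unnamed observer | Patient and observer expectation |
| PONV | Secondary | Nausea is reported; vomiting can be seen | Mainly patient expectation, through nausea |
| Postoperative pain score | Secondary | Patient report (scale not given) | Patient expectation |
| Blood pressure, heart rate | Primary | Instrument | Withdrawal by arm, not reporting |

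**How large could reporting bias be?** The plan gives no event rate for these outcomes and no estimate of bias, so there is no figure of its own to reproduce. What follows is an illustration.

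Inputs:
- n = 20 per group, from Protocol Section 8 and the SAP: 25 × (1 − 0.20) = 20.
- Chi-square or Fisher's exact test at 0.05, from the SAP.
- *Assumed:* each outcome is reduced to yes/no, two arms are compared, and the true rate is 30% in both.
- *Assumed:* knowing the arm shifts the reported rate by 5 or 10 percentage points, either upward in one arm or in opposite directions in the two arms.

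Method: with a and b events in the two arms and t = a + b, the uncorrected statistic is X² = 2n(a − b)² / [t(2n − t)], and the test rejects when X² > 3.84. For example, 8 against 2 events gives 40 × 36 / (10 × 30) = 4.8, which rejects. The rejection probability is the sum of Bin(a; n, p₁) × Bin(b; n, p₂) over all pairs (a, b) that reject. Fisher's test is handled the same way, with p < 0.05 as the criterion.

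| Reported rates | Chi-square | Fisher |
|---|---|---|
| 30% / 30% (no bias) | 0.053 | 0.025 |
| 35% / 30% (one arm, 5 points) | 0.067 | 0.033 |
| 40% / 30% (one arm, 10 points) | 0.104 | 0.059 |
| 35% / 25% (opposite, 5 points each) | 0.110 | 0.061 |
| 40% / 20% (opposite, 10 points each) | 0.291 | 0.192 |

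If all 25 per group were analysed, the last row would be 0.352 and 0.231. A larger sample makes the false difference easier to detect; it does not protect against it. If the SAP intends one overall three-group chi-square, rates of 35/30/25% and 40/30/20% give 0.089 and 0.218 at 20 per group.

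**How large could selective loss be?** The plan allows for 5 of 25 per group to be lost. It does not say how many of these would leave because of their arm, so no bias can be computed. The group-wise summary of withdrawal reasons would show the pattern after the fact but would not prevent it.

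**The case against.** The strongest case against the point has five parts.

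- **Disclosure is not a stated step.** A reader might infer that patients are routinely told their arm before induction, or that withdrawal by group is actively offered. The documents do not say so. Section 17 says only that such requests will be honoured. The supportable statement is that patients can learn their arm and nothing prevents it. This stands.
- **Masking the patient does not remove the bias.** A reader might infer that it could be removed entirely and without extra staff. Someone watching the patient grades injection pain, that person is unnamed and may know the arm, and an independent masked rater might need another person. The documents are silent on staffing, on who records PACU nausea and pain, and on whether an awake patient could tell the syringes apart. This stands: bias is reduced, not removed.
- **The magnitudes are assumed.** The top figure of 0.29 needs opposite shifts of 10 points in each arm. The direction is not settled either: Section 3 associates injection pain with propofol, whereas the Section 11 risk lists name it only under etomidate. This stands, so only a range can be given.
- **The reach is limited.** The patient-dependent outcomes are secondary, the study is called a pilot, and hypothesis 4 and part of hypothesis 3 predict similarity, so a spurious difference would count against them. This stands for reporting bias. A distorted comparison is still a fault whichever way it points, and selective loss is not confined to secondary endpoints.
- **Withdrawal reasons are tabulated by group.** True, but a table does not restore a randomised comparison, and the SAP names no analysis population that would handle it.

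**Conclusion.** The point holds in limited form. The plan has no provision for keeping the arm from the patient, and the Section 17 wording implies that patients can learn it. Three secondary outcomes that feed three of the four hypotheses are therefore open to expectation bias. Group-based withdrawal after randomisation can also unbalance the primary comparisons.

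On the assumed 30% rate with 20 per group, the chi-square false-positive rate moves from 0.053 to somewhere between 0.067 and 0.291 (Fisher: from 0.025 to between 0.033 and 0.192). This shows that a modest shift in reporting matters at this sample size. It does not estimate what will happen in this trial.

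The documents do not support the inference that blood pressure or heart rate readings are themselves subject to patient reporting bias; those endpoints are affected only through who remains in the study. The change is worth making because it is cheap, but the fault does not invalidate the primary analysis.

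**What to change.** 1. In Protocol Section 7, state that the envelope is opened out of the patient's view.
2. State that the arm is not disclosed to the patient until the PACU nausea and pain scores are recorded. Apply the same rule, where practicable, to whoever records those scores.
3. In Section 17, delete randomised group as a named ground for withdrawal. Keep the right to withdraw at any time for any reason.
4. Replace the non-blinded label with a description of a patient-masked trial with an unblinded anaesthetist, and make the consent wording agree.
5. State as a limitation that injection pain is graded by an observer who may know the arm.

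The cost is protocol and consent wording. Drugs, sample size and analysis do not change, and none of these steps in itself adds a person or procedure. The downside is that masking may be imperfect, because the chart or the look of the syringes may reveal the arm, and observer bias in grading injection pain remains.
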